#### IN-PERSON VISIT:

At the beginning of the visit, the lead staff member will give the study participant the In-Person Visit Consent Form, ask her to read it, and give an opportunity for the study participant to ask questions.

IN-PERSON VISIT SURVEY: The subject will be offered \$20 in cash as compensation for completing the survey at the in-person visit. The lead staff member will read an informed consent script before beginning the survey. Verbal consent will be obtained after the consent script is read; the subject will have the opportunity to ask questions prior to giving verbal consent. The consent outlines the purpose, the risks, and the confidentiality procedures in place. Subjects will be informed of the voluntary nature of the study and their ability to skip any question or withdraw at any given time.

#### For Minors (16+ years of age): Baseline Survey Recruitment

Because Room to Grow serves mothers under the age of 18, the research team has decided to expand the study sample to include expectant mothers who are 16+ years of age (though, we expect this to be less than 5% of our sample). After speaking with [name] we have developed and attached a minor assent form and a parent consent form.

If a minor mother is referred and randomized into the study, Columbia staff will be provided with her guardian's phone number (this information comes in with a typical referral). Columbia staff will first contact the guardian and using the Guardian phone script explain the study and ask for permission to contact the minor. If permission is granted, Columbia staff will contact the expectant mother and inform her that her guardian gave us permission for contact, but that the decision to participate in the study is solely hers (this is explained in the Minor phone script).

If the minor agrees to schedule a survey meeting we will coordinate a time that the guardian and minor are home together, as the Columbia interviewer will need to obtain signed consent from the guardian and a signed minor assent form from the expectant mother. During the home visit, Columbia staff will answer any questions the participant or guardian may have and provide them with copies of their consent documents. Following the guardian's consent, the interviewer will ask to conduct the survey with the expectant mother in privacy to ensure her comfort and provide a safe and honest space for participation. Once the interviewer is one-on-one with the expectant mother she will obtain the minor assent form and begin the survey.

In cases where the minor mother is emancipated or if the guardian cannot be reached, Columbia staff will initiate contact by calling her directly; if the subject agrees to participation she will sign the adult ICF and not the minor assent form at the time of the baseline visit.

As with adult participants, minor participants can withdraw at anytime and their participation in the Room to Grow lottery is not contingent on participation in the study.

Consent forms will be translated into Spanish by an approved translator following approval of the English versions by the IRB.

For qualitative interviews and focus groups:

Columbia staff will contact the selection of current RtG participants (all of whom agreed to future contact at the baseline survey), RtG graduates provided by the RtG team, and clinicians. All participants will be informed of the voluntary nature of the qualitative interviews/focus groups and reminded that their participation status will have no impact on their status at Room to Grow. If the participants agree to schedule an appointment/attend a focus group, Columbia staff will coordinate appropriate time slots.

Informed written consent will be obtained at the time of the in-person interview or focus group. Trained research staff will go over all procedures, answer any questions, provide copies of consent forms to all participants and obtain written consent from all participants before beginning data collection.

1/16/18, clarification on RtG clinician recruitment/consent: Clinicians were invited to participate through the RtG director. A RtG Program coordinator arranged a time for each clinician to meet individually with [name] at the RtG NY office for the qualitative interview. [name] met individually with each clinician, presented the study and obtained consent. Clinicians were informed of the voluntary nature of the interview; they did not receive financial incentives as the interviews took place during regular work hours and were approved by the RtG director. Once clinicians agreed to participate interviews were conducted.

**Describe how participants' consent will be obtained and whether an information sheet will be used:**

During the scheduling call, subjects are informed of the voluntary nature of the study and are invited to set up a time to meet for the baseline survey; at the time of the meeting formal written consent will be obtained before proceeding with the baseline survey or any further study participation.

During recruitment for the 10 month follow-up, 25 month follow-up, & 42 month follow-up, subjects who agreed to follow-up at baseline will be called and invited to participate in the follow-up phone survey. Because the survey will be conducted over the phone, interviewers will read an informed consent script and obtain verbal consent from the subject before proceeding with the survey. Subjects will be informed of their right to refuse participation and the right to skip any question. All materials will be translated to Spanish and interviewers who are fluent in Spanish will obtain consent and conduct interviews with Spanish-speaking subjects.

Subjects will be invited to participate in an in-person visit once their child is at least 3 1/2 years old and once they have completed their 42 month follow-up survey. They may refuse to participate in the visit. Written consent for participation in the in-person visit activities with the child (EF-Touch, ROWPVT-4, and the 3 Bag Task) and parent will be obtained at the meeting, which will take place at Columbia University. A separate informed consent script will read to the subject for the in-person follow-up survey. The lead staff member will obtain verbal consent from the subject before proceeding with the survey. Subjects will be informed of their right to refuse participation and the right to skip any question. All materials will be translated to Spanish and interviewers who are fluent in Spanish will obtain consent and conduct interviews with Spanish-speaking subjects. We will obtain written/documented consent if a study participant completes a paper version of our in-person survey and mails it back.

---

**Subject Language**

Enrollment of non-English speaking subjects is expected.

**Languages anticipated: Spanish**

Research Aims & Abstracts
--------------------------------------

**Research Question(s)/Hypothesis(es):**

1) Does random assignment to RtG alleviate parents' experiences of material hardship and financial stress? 2) Does random assignment to RtG enhance the quality of parents' home environment and interactions with children? 3) Does random assignment to RtG enhance parents' connection to essential community and health services?

---

**Scientific Abstract:**

Our research project is to launch a small-scale randomized controlled trial (RCT) of an innovative program in New York City called Room to Grow (RtG). RtG's mission is to enrich the lives of babies born into poverty throughout their critical first three years of development. The research-informed program model combines tailored, one-on-one sessions with an expert clinical social worker in-person every three months plus ongoing communication (phone and email), provision of essential baby items including books, toys, clothing, and equipment (retail value of in-kind items over three years averages

\$10,000), and connections to vital community resources (e.g., housing, entitlements, child care, social services). The goal of RtG's innovative program is to help parents increase the probability that their children will enter school ready to learn and continue on to meet their full potential in education, work, and citizenship. The therapeutic, psychodynamic approach and robust three-year long relationship with families is designed to act as the catalyst for sustainable, long-term change in parenting methods and family system stability. Critically, and in contrast to other programs aimed at improving parenting and child development, RtG believes that providing concrete material assistance enhances the effectiveness of counseling and referrals to low-income families by reducing economic stress and freeing up scarce resources. The program builds on decades of research on the importance of parenting supports for low-income families and their children, the significance of concrete material support and poverty reduction in enhancing children's health and development, and the recognition that the early years are an effective time to provide critical supports that influence long-term outcomes. Numerous programs, such as home-visiting models that provide parenting supports to low-income new mothers have shown promising results (Cates et al., 2016; Peacock et al., 2013). After decades of correlational research establishing relationships between income, poverty, and children's health and development, there is an emerging literature providing convincing causal evidence that income matters for child outcomes (Duncan, Morris, and Rodrigues, 2011; Chaudry and [name], 2016). Both strains of this research build upon additional research that clearly suggests early childhood is a key period of vulnerability where interventions can make a lasting difference in the fortunes of low-income children and their families (Duncan, Magnuson, Kalil, and Ziol-Guest, 2012). Our research will build upon this literature, by testing an intervention that combines *both* parenting supports and meaningful provision of material support - in essence, assessing whether a combined approach can prove potentially more powerful than the sum of its parts.

---

#### **Lay Abstract:**

Room to Grow is a program that provides low-income pregnant mothers with a combination of parenting supports, connection to community-based resources, and direct provision of in-kind supports such as books, toys, strollers, clothes, etc. for their child. Through a small scale randomized controlled trial, we hope to assess whether the program makes an impact on a variety of short-term outcomes related to financial stress, material hardship, and positive parenting behaviors.

---

### **Risks, Benefits & Monitoring**

---

#### **Potential Risks:**

There are two identifiable risks: 1) subjects may experience some distress answering questions and 2) disclosure of information. To protect against the first, the initial script informs subjects that they are free to skip questions that make them feel uncomfortable, they can take breaks at any time, and can stop the interview at any time. Interviewers will have a referral manual if a subject appears to require counseling. Our confidentiality and data protection protocols described in section 10 safe guard against the 2nd risk.

#### **IN-PERSON/HOME VISIT:**

The two identifiable risks are (1) distress about the in-person/home visit and (2) disclosure of information about the subject.

(1) Distress about the in-person visit – Although the in-person/home visit activities are similar to activities carried out in everyday life, a study participant might feel self-conscious about having strangers come into her home, or be embarrassed participating in a study in person. Lastly, the parent might become embarrassed or annoyed if the child has trouble focusing on the activities or becomes upset or acts out in some way. To protect against this risk, the staff will:

 Emphasize that all activities in the visit are voluntary and they can skip or withdraw from any activity.  Offer to schedule the visit on campus if the study participant has any hesitation about inviting staff to her home.

 Tell the study participant before the ROWPVT-4 that the activity may become more difficult over time and people are not expected to get all the answers right.

 Be patient with a child who is distractible, re-direct his/her attention back to the activity, and suggest taking a short break if the child becomes upset or is having great difficulty focusing.

(2) Disclosure of information about the subject -- To protect against this risk, staff will follow the data security measures described in the Privacy and Data Security section.

---

#### **Potential Benefits:**

There are no direct benefits to subjects from participating in the study. We hope that the study will help Room to Grow be most effective in its work going forward and also provide information on poverty and child development to policy makers working to better serve low-income mothers and children.

### RISK/BENEFIT DETERMINATION

#### Baseline Participation:

Only mothers who are 16+ years of age will have the opportunity to participate in the study. First, if the guardian can be reached, the Columbia team will obtain their consent to contact the minor. If the minor agrees to a survey appointment, the home visit will be scheduled at a time that the minor and guardian are both home--they will both sign consent/assent documents and will be provided with copies for their records. Columbia staff will emphasize the voluntary nature of the study, answer any questions, and ensure that the participant is in a private and safe space during the survey and assent signing. The survey will 30-45 minutes and the topics are relatively neutral; we do not anticipate distress, but will have a manual with resource referrals if necessary. [name] (PI) spoke with [name] about the inclusion of expectant mothers who are 16+ years of age in the study.

#### In-person visit:

The child will participate in up to 3 study components: four game-like activities on a laptop, a vocabulary activity using a picture cue book, and one videotaped activity in which the child plays with the parent using researcher-provided toys and a book. These study components are similar to activities that are commonly part of a young child's life.

### ASSENT OF SUBJECTS

#### Baseline:

All minors in this study will be 16+ year old expectant mothers in their third trimester of pregnancy and the questions are about their circumstances--we expect them to fully understand all survey topics. We expect less than 5% of our sample to fall into this category.

#### In-person Visit:

None of the children participating in the in-person visit are expected to be capable of providing assent. The children will be ages 3 ½ to 5 years old when they participate in the in-person visit.

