Additional funding has allowed for the expansion of recruitment size; the current goal is to recruit 160 treatment group subjects and 160 control group subjects. Treatment and control group subjects will both be given an incentive of \$50.00 in cash for their participation in the survey, and control group subjects will also be given a gift basket filled with approximately \$75.00-\$100 worth of developmentally-appropriate gifts for their impending child (items are purchased from Amazon, and prices vary depending on when items are purchased). Approximately, four business days after the in-home visit, Columbia staff will let control group participants know that they were not selected for the Room to Grow Program; subjects in the treatment group will receive follow-up from Room to Grow. Experienced interviewers will conduct the interviews in either English or Spanish. Subjects will be enrolled in the "Columbia Moms and Babies Study" and follow-up permission and information will be collected during the baseline visit (i.e., subjects will be asked for best modes of future contact and have the opportunity to provide friends' and family members' contacts, email addresses, etc.). Additionally, to inform understanding of program operations and potential outcomes, 9 RtG program graduates will be invited to participate in Focus Groups; 20 RCT participants will be randomly selected and invited to participate in qualitative interviews; the three clinicians at Room to Grow will be invited to participate in qualitative interviews. An in-person visit will be completed with enrolled subjects that have completed the 42M phone survey, once the subject's focal child is at least 3 ½ years old. At the end of the 42M survey, study participants are informed of an opportunity to participate in the in-person visit conducted by the Columbia study team at the School of Social Work. We will also offer study participants the option to have the in-person visit take place in their home. New York City residents will be eligible for the visit. We will also have a handful of subjects who no longer live in NYC during the in-person visit phone contact. If any one of these subjects are living outside of NYC & are within reasonable traveling distance to/from Columbia University's School of Social Work or Nash Building, they too will be eligible for the visit.

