#### **Receptive Language Skills:**

ROWPVT: The test offers a quick and reliable measure of an individual's understanding of English-speaking vocabulary, which is assessed by asking the individual to point to named objects, actions, and concepts pictured in illustrations. The ROWPVT is a standardized language assessment based on a mean of 100 and a standard deviation of 15. Scores of 85-115 are considered to be within the average range of functioning. Scores above 115 are considered above average and scores below 85 are considered below average. Scores from this measure indicate that a child's receptive vocabulary is above average, below average, or equivalent to their same age peers.

ROWPVT: Spanish-Bilingual Edition (ROWPVT: Spanish-Bilingual Edition) is a standardized specific language assessment based on a mean of 100 and a standard deviation of 15. The assessment was norm referenced on typically developing individuals who are proficient in both Spanish and English. The examinee has the option to respond in English or Spanish and instructions are provided in both languages. The purpose of this assessment is to evaluate an individual's overall Receptive vocabulary (i.e. what he/she comprehends) skills when given the opportunity to utilize both languages. The examinee is presented with a picture scene, the examiner then verbally presents a word and the examinee must then point to the picture that corresponds with the word. This is a standardized language assessment based on a mean of 100 and a standard deviation of 15. Scores of 85-115 are considered to be within the average range of functioning. Scores above 115 are considered above average and scores below 85 are considered below average. Scores from this measure indicate that a child's receptive vocabulary is above average, below average, or equivalent to their same age peers.

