#### **Working Memory Span (EF-Touch: Houses game)**

This task measures working memory and is based on work from Kane & Engle, 2003. Working memory involves holding information in short-term storage and attending to one item while overcoming interference from the other. In this task, children are presented with pictures of houses with animals and colors in them. The child is asked to name the type of animal and color in each of the houses and then, after a short delay, the house is presented again - but this time the house is empty. The child is asked to recall only one piece of information (e.g., either the color or the animal that was in the house). The task requires children to perform the operation of naming and holding in mind two pieces of information simultaneously and to activate one while overcoming interference occurring from the other. The task becomes more difficult as the number of houses increases. In the pretest phase, it is established that children can name both the colors and the animals in the task. Children then receive three 1-house trial, three 2-house trials, and three 3-house trials. There are 18 items. The score on this activity is a proportion from 0 to 1, zero indicating no items correct and 1 indicating all items were correct.

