#### **Inhibitory Motor Control (EF-Touch: Pigs game)**

This task measures inhibitory motor control and is a standard go no-go task (Durstun, Thomas, Yang, Ulug, Zimmerman, & Casey, 2002). Children are presented with a large green button on the screen that makes a "popping" sound when it is touched. Children are instructed to touch the button every time that they see an animal (the 'go' response) except when that animal is a pig (the 'no-go' response). No-go responses vary in difficulty depending on how many go responses preceded them. In the pretest phase, children are asked to identify all of the animals. During administration items, the task is presented in varying numbers of go trials prior to each no-go trial, including, in standard order, 1-go, 3-go, 3-go, 5-go, 1-go, 5-go, 7-go and 7-go. There are 40 items. The score on this activity is a proportion from 0 to 1, zero indicating no items correct and 1 indicating all items were correct.

Statistical procedures will include comparisons of outcomes between the treatment and control groups. Given the small nature of the sample, and concomitantly limited statistical power that entails, our analyses will focus on understanding patterns of associations across outcomes rather than a strict focus on statistical significance. That said, formal tests of significant differences will still be performed.

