#### 10 Month Follow-Up Recruitment Strategy

Using the subject's projected due date, Columbia staff will initiate phone contact with subjects who agreed to be contacted for follow-up approximately one week before their baby is 10 months old. Columbia interviewers will use contact information that was collected at baseline (provided by the subject at the time of the interview) as well as any updated contact information that the subject may have provided with the jotter outreach letter. For adult participants, interviewers will call and remind subjects of the purpose of the study, describe what the follow-up entails and invite them to participate using the attached 10M Adult phone pitch. The subject can agree to participate at the time of the call or can schedule the survey at a later time. A subject is free to refuse participation in the follow-up. If the subject agrees, a consent script will be read verbatim and verbal informed consent will be obtained at the start of the survey (see attached 10M Phone Consent). For subjects that were below the age of 18 at baseline, interviewers will ask their current age--for those who have turned 18 since the baseline guardian contact/permission will not be attempted. For subjects who are still under the age of 18, the interviewer will ask for the guardian's contact information (see attached 10M Pitch Minor). However, in the event that the minor cannot provide the guardian's information, the interviewer will proceed with obtaining consent from the minor. We will do our best attempt guardian contact for minors, however, because all minors who are enrolled in the study received guardian consent at baseline and because the minors have given birth since baseline, we will proceed with allowing the minor to consent to participation if the guardian is not available.

Worth noting is that in NYC the following exemption applies to minors who are pregnant and/or parents:

- "The child must get a parent's permission to get routine health care unless it is an emergency or for sexually transmitted disease, family planning services, drug treatment or mental health treatment. The child does not need a parent's permission if the child is pregnant, a parent, or married." - NYlaw.org

Once we make contact with the subject on the phone we will use previously approved protocols to pitch, schedule and complete the 9-10 month survey with the subject's consent.

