At the end of the 42M survey, which is administered after the focal child turns 3 ½ years old, each subject (not including primary caregivers) is asked if they would be interested in participating in an in-person visit that includes assessments for their child at a later date.

The wording of the question is as follows:

"Thank you for your responses. As part of the study, we would like to arrange an in-person visit with you and your child at Columbia University. The visit includes age appropriate assessments with your child using a Touch Screen laptop and a video-recorded play session. We are offering \$80 for your participation in the visit, as well as an incentive to compensate for your travel time. Is this something you would be willing to participate in? Do you have any questions or thoughts at this time?"

YES

NO

MAYBE/NOT SURE"

TELEPHONE: If the participant answers yes to this question, study staff will call and will schedule the visit if the participant is interested. If the study participant answers maybe, study staff will call and ask if they would be interested in hearing more. A separate document, Scheduling Script, provides the script used for arranging the in-person visit after study participants have expressed interest in participating. Study staff can also use text as a way to also pitch the visit.

EMAIL: Should study staff be unable to reach the participant via phone, staff will email the participant all pertinent information from the scheduling script. Staff will only use the email address that was provided by the participant as a mode of communication/contact.

---

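### The executive-function scores have no age norm and the visit has no upper age limit, so age at testing adds noise that a prespecified age covariate would remove

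*Combined protocol and SAP*

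**What the plan says.** All references are to the combined protocol and SAP.

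- **Scoring.** The Houses task (Working Memory Span) is scored thus: "The score on this activity is a proportion from 0 to 1, zero indicating no items correct". Something's the Same (Attention-Shifting Performance) and Pigs (Inhibitory Motor Control) use the same scale. None of the three descriptions mentions an age norm. The vocabulary test, under Receptive Language Skills, is by contrast a "standardized language assessment based on a mean of 100 and a standard deviation of 15", read against children of the same age.
- **Timing of the visit.** Study Design places the visit "once the subject's focal child is at least 3 ½ years old". The in-person visit part of the recruitment section says that mothers are asked, when the 42-month survey ends, about an "in-person visit that includes assessments for their child at a later date". Neither place gives an upper age or a target window. The only upper figure is in Assent of Subjects, which expects children aged 3½ "to 5 years old when they participate in the in-person visit".
- **Analysis.** The paragraph that closes the measures section reads: "Statistical procedures will include comparisons of outcomes between the treatment and control groups". It adds that power is limited and that significance tests will still be done. It names no model and no covariate for any outcome.
- **Milestones.** Calls for the 10- and 25-month surveys, which carry the parent-reported milestones, are timed from the "projected due date, Columbia staff will initiate phone contact with subjects who agreed to be contacted for follow-up".

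**The concern.** Eighteen months is a wide span at this age. If older children score higher on these tasks, part of the spread in each score reflects only when the child was tested. The vocabulary score is largely protected by its age-referenced scale; the three executive-function scores are not. A comparison that ignores age leaves that spread in the error term, in a trial whose authors already describe its power as limited.

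A second and separate risk is that one arm might be seen systematically earlier than the other. The executive-function contrast would then include an age effect that could be read as a programme effect. No provision in the plan would prevent, reveal or correct this.

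**Working it through.** The plan gives no effect size, standard deviation, age slope, age distribution or expected number of visits, so there is no figure of its own to reproduce. What follows is an illustration.

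**Inputs from the documents:** ages 3½ to 5 years, a span of 18 months (Assent of Subjects); 160 enrolled per arm (Study Design and Statistical Procedures).

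**Assumed:** ages uniform over the span; correlation r between age and score of 0.1 to 0.3, with 0.5 as a high case; two-sided 5% tests; 80 children per arm attending, as an alternative to all 160.

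**1. Spread of age.** SD = 18/√12 = 5.20 months.

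**2. Noise.** Leaving age out multiplies the standard error by 1/√(1 − r²).

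| r | Standard error ratio | Share of sample size retained, 1 − r² |
|---|---|---|
| 0.1 | 1/√0.99 = 1.005 | 99% |
| 0.3 | 1/√0.91 = 1.048 | 91% |
| 0.5 | 1/√0.75 = 1.155 | 75% |

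The same can be put as a slope b, in within-age SD per month, with variance inflation 1 + (5.20b)². For b = 0.02, 0.04 and 0.06 this is 1.011, 1.043 and 1.097, corresponding to r of about 0.10, 0.20 and 0.30. At 160 per arm, power for an effect of 0.313 SD falls from 80.0% to 79.6%, 78.3% and 76.3%. If visits cluster more tightly, with an age SD of 3.0 months, the inflation is only 1.004, 1.014 and 1.032.

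**3. Systematic difference in timing.** Shift = b × difference in mean age. For 2 months this is 0.04, 0.08 and 0.12 SD. The detectable difference at 80% power is (1.960 + 0.842) × √(2/n), which is 0.313 SD at 160 per arm and 0.443 SD at 80. The largest shift is therefore 0.12/0.313 = 38% or 0.12/0.443 = 27% of it. With no true effect, a systematic 2-month difference raises the 5% rejection rate as follows.

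| Per arm | b = 0.02 | b = 0.04 | b = 0.06 |
|---|---|---|---|
| 160 | 6.5% | 10.8% | 17.6% |
| 80 | 5.7% | 7.9% | 11.2% |

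**4. What chance alone would do.** The standard error of the difference in mean age is 5.20 × √(2/n), or 0.58 months at 160 per arm and 0.82 at 80. The 95% limits are ±1.14 and ±1.61 months. A 2-month difference is 2/0.58 = 3.4 or 2/0.82 = 2.4 standard errors, so the case in step 3 needs a systematic cause.

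**The case against.** The strongest reply is that the cost is small and the bias hypothetical. Much of that stands. Over r = 0.1 to 0.3 the standard error grows by 5% at most. Every input beyond the age span and enrolment is assumed, including that these tasks depend on age at all. The range in the assent section states expected ages, not a distribution. None of the three research questions concerns child executive function.

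Several stronger readings are tempting, and the documents do not support them.

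- **Any difference in age between arms is bias.** A chance difference under randomisation is sampling error, already reflected in the standard error. Only a systematic difference biases the contrast.
- **The programme's contact with treatment families would bring them in earlier.** The programme lasts three years and the visit comes at 3½ or later, so on schedule that contact has ended. Study staff arrange visits for both arms with one script, using contact details that the study itself collects. A lasting difference in how easily families are reached is possible, but nothing shows it.
- **The plan has chosen an unadjusted analysis.** It says only that comparisons will be included; it is silent on covariates for every outcome.
- **Calls timed from the due date bias the milestone results.** That rule applies equally to both arms and fixes only when calling begins. No milestone score is defined from which age sensitivity could be judged.
- **The three-bag scales need age terms too.** The two named scales rate the parent's behaviour, and the documents give no reason to expect dependence on the child's age.

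One technical objection also deserves weight: age at assessment is fixed after randomisation. If the programme altered who was seen late, conditioning on age could bring in some selection. That is a reason to show both analyses, not to omit age.

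**Conclusion.** The point holds as one of precision. Three outcomes without age norms are to be collected over an expected 18-month age range, with a lower age bound only and no stated allowance for age. If ages are uniform, the standard error is about 0.5% to 5% larger than necessary at assumed correlations of 0.1 to 0.3, and about 15% at 0.5; tighter clustering of visits makes it less.

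Bias is conditional. It requires a systematic timing difference, which the documents neither show nor guard against. A 2-month difference would shift the contrast by 0.04 to 0.12 SD on the assumed slopes. A reader should not infer from this that the executive-function comparison is biased. This is an inexpensive improvement to a secondary part of the trial and does not threaten its main questions.

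**What to change.** In the analysis section:

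- Prespecify the child's exact age at assessment, calculated as visit date minus actual birth date, as a covariate in the models for the three EF-Touch scores. State the form of the age term in advance. The gain in step 2 is realised only as far as that form fits.
- Report mean age at assessment by arm, so that any difference in timing is visible.
- Show the unadjusted comparison alongside.
- Optionally, treat age at interview in the same way for the 10- and 25-month parent-reported milestones, as a precision measure only.

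The cost is a few sentences. No new data should be needed. The linkage section already lists the child's birth date among its matching fields, and the vocabulary test needs the child's age at the visit for its starting point and standard score. Because linkage is subject to separate consent, the team should confirm that birth date and visit date are held for every child seen. Writing the covariate in beforehand also prevents the choice of age adjustment from being made after the results are known.
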